Nivolumab will be administered at approximately 2 week intervals for up to 1 year.

5.3 Dose modifications during phase II:

Patients who experience nivolumab-specific (defined as determined by the principal investigator) grade 3-4 extramedullary toxicities during induction cycle #1, and who are not in CR after cycle #1, may receive a second induction course at a similar or lower dose level with respect to idarubicin and cytarabine. Other dose modification schedules felt to be in the best interest of the patient may be permitted, after discussion with the principal investigator. There will be no dose modifications of idarubicin or cytarabine for either induction cycle #1, or second induction course, secondary to myelosuppression. There will be no dose reduction with respect to Nivolumab but dose delays or interruptions are permitted after discussion with the PI.

5.4 Administration guidelines for nivolumab: Nivolumab will be administered by IV infusion over approximately 60 minutes \pm 10 minutes. The recommended infusion duration for the product is 60 minutes and every effort should be made to adhere to this time as closely as possible.

5.5 No dose reduction is allowed for Nivolumab. Dose delays and interruptions should follow the guidance in section 6.10.3.

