5.6 Myelosuppression

Patients with acute leukemia usually present with abnormal peripheral blood counts at the time therapy is started, and myelosuppression is an expected event during the course of therapy for acute leukemias and myelodysplastic syndromes. Thus, no dose adjustments or treatment interruptions for myelosuppression will be planned for the first 6 weeks of therapy. After this time, treatment interruptions and dose adjustments may be considered according to the following guidelines:

Patients with neutropenia or thrombocytopenia as a consequence of the disease prior to the start of therapy do not require treatment interruptions for myelosuppression. Dose reductions of the chemotherapy agents in these patients should be considered on an individual case basis and discussed with the PI.

Nivolumab is not associated with myelosuppression – it can be held if necessary but no dose reductions are needed after resumption

- 5.7 **Dose adjustments for only one of the drugs** can be made if, in the opinion of the treating physician, the toxicity is attributable to one of the drugs.
- 5.8 Patients who show no significant anti-tumor effect (i.e. no CR or CRp) after 2 courses will be taken off the study.
- 5.9 **Remission Consolidation/Maintenance:** Patients achieving a CR or CRp may receive consolidation maintenance therapy as follows:
 - a. Consolidation – Up to 5 additional courses as follows:
 - Idarubicin 8 mg/m² IV over 15 to 30 minutes daily x 2 days (or the final induction dose, whichever is lower).(days 1-2)
 - Ara-C 0.75 g/m² IV over 24 hours daily x 3 days (or the final induction dose, whichever is lower) (days 1-3)
 - Nivolumab dose as per induction IV every 2 weeks as a continuation of the induction treatment.
 - Solumedrol 50-100 mg or dexamethosone 10 mg IV daily x 3 days with ara-C (days 1-3)
 - courses given every 4-6 weeks upon recovery of counts and toxicities
 - b. Maintenance – Nivolumab will be administered every 2 weeks for up to 1 year with no breaks except for toxicity. Maintenance will only be administered in patients in CR or CRp.
 - c. Consideration of allogeneic transplant in CR. Patients eligible for allogeneic.

SCT will be evaluated for the procedure, if felt to be in their best interest. Therapy with nivolumab will be discontinued at least approximately one week prior to admission for the transplant procedure.

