comfortable that the symptoms will not recur. Nivolumab will be permanently discontinued. Institutional guidelines will be followed for the treatment of anaphylaxis. Remain at bedside and monitor subject until recovery from symptoms. In the case of late-occurring hypersensitivity symptoms (e.g. appearance of a localized or generalized pruritus within 1 week after treatment), symptomatic treatment may be given (e.g. oral antihistamine or corticosteroids).

For further details regarding dose-calculation of nivolumab, preparation and dispensing of nivolumab, administration of nivolumab please see the dosing procedure manual.

5.10.3 Nivolumab dose delay for immune-oncology drug-related adverse events, clinically significant in the opinion of the investigator

Nivolumab administration should be delayed for the following drug-related AEs:

- Any Grade >2 non -skin AE, except that
 - Grade 2 fatigue or laboratory abnormalities do not require delay, however
 - ◆ For a subject with baseline AST, ALT, or total bilirubin within normal limits, delay dosing for drug-related Grade >2 values
- Any Grade 3 skin AE, or Grade 3 laboratory abnormality, with the following exceptions:
 - Grade 3 lymphopenia or leukopenia does not require dose delay.
 - If a subject has Grade 1 baseline AST, ALT, or total bilirubin, delay dosing for drug-related Grade 3 toxicity
- Any AE, laboratory abnormality, or intercurrent illness, which in the judgment of the investigator, warrants delaying the dose of study medication.
- Nivolumab dose reductions are not permitted in this study (only dose delays when indicated).

Detailed management algorithms for immune-oncology drug-related adverse events (including gastrointestinal, renal, pulmonary, hepatic, endocrine, skin and neurological) are provided in Appendix E. These general guidelines constitute guidance to the Investigator and may be supplemented by discussions with the Medical Monitor representing the Sponsor. If the criterion to resume treatment is met, the subject should restart treatment at the next scheduled time-point per protocol.

Criteria to Resume Treatment:

Subjects may resume treatment with study drug when the drug-related AE(s) resolve to Grade ≤1 or baseline value, with the following exceptions:

- Subjects may resume treatment in the presence of Grade 2 fatigue
- Subjects who have not experienced a Grade 3 drug-related skin AE may resume treatment in the presence of Grade 2 skin toxicity

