- Subjects with baseline Grade 1 AST/ALT or total bilirubin who require dose delays for reasons other than a 2-grade shift in AST/ALT or total bilirubin may resume treatment in the presence of Grade 2 AST/ALT OR total bilirubin
- Subjects with combined Grade 2 AST/ALT AND total bilirubin values meeting discontinuation parameters (Discontinuation Section below) should have treatment permanently discontinued
- Drug-related pulmonary toxicity, diarrhea, or colitis, must have resolved to baseline before treatment is resumed
- Drug-related endocrinopathies adequately controlled with only physiologic hormone replacement may resume treatment

If the criteria to resume treatment are met, the subject should restart treatment at the next scheduled timepoint per protocol. However, if the treatment is delayed past the next scheduled timepoint per protocol, the next scheduled timepoint will be delayed until dosing resumes.

If treatment is delayed > 6 weeks, the subject must be permanently discontinued from study therapy, except as specified in discontinuation section.

Nivolumab Discontinuation Criteria:

Treatment should be permanently discontinued for the following:

- Any Grade 2 drug-related uveitis or eye pain or blurred vision that does not respond to topical therapy and does not improve to Grade 1 severity within the re-treatment period OR requires systemic treatment
- Any Grade 3 non-skin, drug-related adverse event lasting > 7 days, with the following exceptions for drug-related laboratory abnormalities, uveitis, pneumonitis, bronchospasm, diarrhea, colitis, neurologic adverse event, hypersensitivity reactions, and infusion reactions:
 - Grade 3 drug-related uveitis, pneumonitis, bronchospasm, diarrhea, colitis, neurologic adverse event, hypersensitivity reaction, or infusion reaction **of any duration** requires discontinuation
- Grade 3 drug-related laboratory abnormalities do not require treatment discontinuation except those noted below:
 - Grade 3 drug-related thrombocytopenia > 7 days or associated with bleeding requires discontinuation
 - Any drug-related liver function test (LFT) abnormality that meets the following criteria require discontinuation:
 - AST or ALT > 8 x ULN
 - Total bilirubin > 5 x ULN
 - Concurrent AST or ALT > 3 x ULN and total bilirubin > 2 x ULN

- Any Grade 4 drug-related adverse event or laboratory abnormality, except for the following events which do not require discontinuation:

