8.0 Evaluation During Study

- 8.1 CBC, platelet, differential (if WBC $> 10^9/L$) every 4-7 days during remission induction and every 1 to 4 weeks during maintenance therapy.
- 8.2 Bone marrow aspirate and cytogenetics and molecular studies (if abnormal at start) on day 21-28; then aspirate every 1-2 weeks as required until CR; then every 3-6 months in year 1 if deemed necessary by the treating physician. Bone marrow aspiration may be omitted in patients where there is clear evidence of active disease (e.g., persistent blasts in peripheral blood).
- 8.3 Creatinine, total bilirubin and SGPT, PT, PTT, and INR every 1-2 weeks during induction then every 4-8 weeks on study.
- 8.4 Blood samples (10cc)/bone marrow (optional studies, see Section 14)
- 8.5 End of Study: History and physical exam
End of study evaluation will be performed after the completion of the maintenance therapy, or any time before that if the patient withdraws from the study or the treatment is discontinued for toxicity or disease relapse/progression.

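### After induction, scheduled liver tests come every 4-8 weeks against 2-weekly nivolumab, and AST is never scheduled, so the liver-based hold, restart and stop rules lack a fresh value for about half to three quarters of doses

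*Combined protocol and SAP*

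**What the plan says.** Section 5.10.3 has three layers of liver rule for nivolumab.

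- **Delay.** Drug-related laboratory toxicity holds the dose: "Any Grade 3 skin AE, or Grade 3 laboratory abnormality, with the following exceptions". The liver branches of this rule are written for normal and Grade 1 baselines of AST, ALT or bilirubin.
- **Restart.** "Subjects may resume treatment with study drug when the drug-related AE(s) resolve to Grade ≤1 or baseline value". There is one liver relaxation, for "Subjects with baseline Grade 1 AST/ALT or total bilirubin who require dose delays for reasons other than a 2-grade shift".
- **Permanent stop.** One trigger is "AST or ALT > 8 x ULN". Others are total bilirubin above 5 x ULN, and AST or ALT above 3 x ULN together with bilirubin above 2 x ULN. Section 5.11 repeats the combined criterion.

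Dosing is 2-weekly. Section 5.2 b says "Nivolumab will be administered at approximately 2 week intervals for up to 1 year" and section 5.9 b says "Nivolumab will be administered every 2 weeks for up to 1 year with no breaks except for toxicity". Section 5.9 a continues the same 2-weekly nivolumab through up to five consolidation courses of idarubicin and cytarabine.

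The tests are set by section 8.3: "Creatinine, total bilirubin and SGPT, PT, PTT, and INR every 1-2 weeks during induction then every 4-8 weeks on study". The calendar in section 6.1 agrees, and adds weekly tests for four weeks in the first course. SGPT is the only transaminase named in section 7.2, section 8.3 or the calendar.

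**The concern.** A rule that acts on a laboratory value works only if the value is there when the dose decision is made. During induction the schedule provides this for ALT and bilirubin. From consolidation on it does not: dosing stays 2-weekly while the liver tests move to every 4-8 weeks. A drug-related ALT rise that calls for a delay, or even for permanent discontinuation, can be followed by more nivolumab before any scheduled test shows it.

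The gap does not need an unusual patient. It applies to someone with normal liver tests at entry. It also covers the consolidation courses, whose chemotherapy the protocol itself lists as hepatotoxic: section 13.2.5 gives a 44% frequency of bilirubin and transaminase elevations for idarubicin, and section 13.3.5 lists acute transaminase increases for cytarabine.

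AST is a separate gap. The delay, restart and stop rules refer to AST, some of them to baseline AST, but no section schedules it before or during the study.

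**Working it through.** **Inputs**
- First nivolumab dose about day 24 (5.2, 5.10), then every 14 days for up to 1 year (5.2 b, 5.9 b).
- Minimum interval between doses 12 days (13.1.6).
- Liver tests every 1-2 weeks in induction, then every 28-56 days (8.3, calendar).
- Induction of one or two cycles of 28-35 days (5.2), so it is assumed to end on day 28, 35, 2 x 28 = 56 or 2 x 35 = 70.

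The plan gives no figure for doses per liver test, so there is nothing to reproduce first.

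**Doses per scheduled value** = test interval / dose interval.
- 28/14 = 2 and 56/14 = 4.
- At the 12-day minimum interval the counts become 2-3 and 4-5, so 4 is not a strict maximum.
- In induction, with tests every 7-14 days and 14-day dosing, no value covers more than 1 dose.

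**Total doses.** Doses fall on day 24 + 14k.
- If the year is counted from day 1, the last dose has k = floor((365 - 24)/14) = 24, which gives 25 doses.
- If it is counted from the first nivolumab dose, the last has k = floor(365/14) = 26, which gives 27 doses.

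**Post-induction doses without a new scheduled test.** Let n be the number of doses after induction ends. Assume the first of them has a test and every later test falls on a dose day. The number with no scheduled test since the previous dose is then n - ceil(n/2) for 4-weekly tests and n - ceil(n/4) for 8-weekly tests. Each cell gives the two ways of counting the year (from day 1 / from the first nivolumab dose).

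| Induction ends, day | n | Untested, 4-weekly | Untested, 8-weekly |
|---|---|---|---|
| 28 or 35 | 24 / 26 | 12 / 13 | 18 / 19 |
| 56 | 22 / 24 | 11 / 12 | 16 / 18 |
| 70 | 21 / 23 | 10 / 11 | 15 / 17 |

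For 4-weekly tests the share runs from 10/21 = 48% to 12/24 = 50%. For 8-weekly tests it runs from 15/21 = 71% to 18/24 = 75%.

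**The restart wording, read against the other rules.** This part is textual.
- With a Grade 2 baseline, restart at baseline is by definition below Grade 3, and a drug-related Grade 3 value requires a delay.
- With ALT above 3 x ULN and bilirubin above 2 x ULN, the combined stop applies at any baseline.
- What is left is an isolated ALT elevation in a patient whose baseline is already Grade 3. Suppose ALT is 6 x ULN at baseline (Grade 3 if that grade starts above 5 x ULN; the cut-off is assumed, since the documents do not print it). ALT rises to 7.5 x ULN on treatment and returns to 6 x ULN with normal bilirubin. The restart sentence is met. The Grade 3 delay rule arguably still says hold, unless the 6 x level is put down to the earlier abnormality. Section 5.10.3 does not say which prevails.

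**The case against.** The strongest reply is that 4-8 weeks is a routine schedule and does not limit testing. Investigators may order extra tests, and 5.10.3 lets them delay for any laboratory abnormality they judge to warrant it. A leukemia unit giving chemotherapy is likely to test more often than the calendar requires. All of that is true. But a judgment clause can act only on a value someone has obtained, and the plan leaves that value to chance for up to three consecutive doses between 8-weekly tests.

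A second reply is that hepatic events are managed under Appendix E, which is not in the text available. This limits what can be said. A reader might infer that a patient restarted after a hepatic hold will receive several doses on one value. The documents do not show that, because retesting around a hold may be set in Appendix E. However, 5.10.3 describes the appendix as algorithms for managing drug-related events. The routine gap before an abnormality is found does not depend on it.

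A third reply is that ALT alone usually triggers the rules, since the stop criteria read AST or ALT. That makes the missing AST less serious, but the branches that depend on baseline AST still have no scheduled input.

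A reader might also infer from the restart sentence that a patient with a raised baseline faces no limit below 8 x ULN. That does not hold. The Grade 3 laboratory delay carries no exemption for a raised baseline, the combined ALT and bilirubin stop sits lower, and a Grade 2 baseline bounds itself below Grade 3. Section 4.5 also caps entry SGPT at 2.5 x ULN unless the elevation is attributed to leukemia.

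**Conclusion.** The schedule gap is real and can be read directly from the text. After induction, one scheduled ALT and bilirubin value covers 2 to 4 nivolumab doses, and about half (4-weekly) to three quarters (8-weekly) of those doses have no scheduled liver test since the previous one. AST is not scheduled at any point. The counts assume 14-day dosing, a completed year, induction ending between day 28 and day 70, and tests aligned with doses.

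The restart wording is a minor matter. It leaves an unresolved conflict between two clauses for isolated ALT with a Grade 3 baseline. The documents do not say how many patients that would be, and the number is probably small. Because "Maintenance will only be administered in patients in CR or CRp", a prestudy elevation blamed on leukemia would no longer be the expected level by then.

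This is a patient-safety improvement that should be made because it is cheap. It changes no endpoint, sample size, error rate or operating characteristic.

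**What to change.** 1. In section 8.3 and the calendar, add SGPT, AST and total bilirubin within about 3 days (a suggested window) before each nivolumab dose, including the first, with the result reviewed before dosing.
2. Add AST to the prestudy tests in section 7.2 and the calendar, so that the rules referring to baseline AST have a value to use.
3. As a clarification only, state in 5.10.3 that for an isolated ALT elevation with a Grade 3 baseline the Grade 3 laboratory delay prevails over restart at the baseline value, whatever the baseline elevation is attributed to.

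The cost is one calendar line, one added prestudy test and one sentence, plus about 10-19 extra liver panels for a patient who completes the year. That count assumes the existing 4-8 weekly draws are moved to dose visits. CBC is already drawn every 1-4 weeks in this phase, so many panels can share a draw. The third change may keep a few patients with a persistently high ALT off nivolumab for longer, which is what the existing delay rule appears to intend.

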 - Isolated Grade 4 amylase or lipase abnormalities that are not associated with symptoms or clinical manifestations of pancreatitis and decrease to < Grade 4 within 1 week of onset.
 - Isolated Grade 4 electrolyte imbalances/abnormalities that are not associated with clinical sequelae and are corrected with supplementation/appropriate management within 72 hours of their onset
- Any dosing interruption lasting > 6 weeks with the following exceptions:
 - Dosing interruptions to allow for prolonged steroid tapers to manage drug-related adverse events are allowed. Prior to re-initiating treatment in a subject with a dosing interruption lasting > 6 weeks, the Investigator must be consulted. Tumor assessments should continue as per protocol even if dosing is interrupted
 - Dosing interruptions > 6 weeks that occur for non-drug-related reasons may be allowed if approved by the Investigator. Prior to re-initiating treatment in a subject with a dosing interruption lasting > 6 weeks, the Investigator must be consulted. Tumor assessments should continue as per protocol even if dosing is interrupted
- Any adverse event, laboratory abnormality, or intercurrent illness which, in the judgment of the Investigator, presents a substantial clinical risk to the subject with continued nivolumab dosing

5.11

Definition of Dose Limiting Toxicity (DLT)

Dose-Limiting Toxicity will be graded according to the NCI Common Toxicity Criteria version4.03. See NCI Common Toxicity Criteria for definitions of DLT by organ system.

- a) All \geq grade 3 drug-related, clinically significant non-hematologic toxicities will be considered DLTs. A study drug-related occurrence of an elevation in AST/ALT $> 3 \times$ ULN and concomitant Bilirubin of $> 2 \times$ ULN is a Dose Limiting Toxicity and patients meeting this criteria should be permanently discontinued from study treatment (nivolumab).
As the following are common events in patients with leukemia (> 50%), they will not be used for the definition of MTD and DLT, nor will they be reported as ADRs: low blood pressure due to dehydration requiring fluid replacement, abnormalities of LDH (lactate dehydrogenase) and alkaline phosphatase, disturbances in electrolytes (magnesium, phosphorus,

calcium), alopecia, nausea and vomiting (if manageable with supportive care measures).

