b) Grade 3 hematologic toxicity (criteria for leukemia on the CTC version 3.0) lasting for 6 weeks or more after interruption of therapy with a hypocellular bone marrow and no marrow blasts. Anemia will not be considered a hematologic DLT. As the following are common events in patients with leukemia (> 50%), they will not be used for the definition of MTD and DLT, nor will they be reported as ADRs: prolonged myelosuppression (grade 3 - 4), neutropenic fever without infection (grade 3), non-neutropenic fever (grade 3), infections with grade 3 and 4 neutropenia, infections without neutropenia (grade 3), readmission associated with NCI grade 3 toxicity cytopenias not resulting in death, transfusions of platelets and packed RBCs (grade 3).

5.12

Concomitant medications: In the event of severe anemia, thrombocytopenia or neutropenia, patients may receive appropriate supportive care (e.g., transfusions, prophylactic antibiotics, antifungals and/or antivirals, hematopoietic growth factors). In the event of high white blood cell (WBC) counts, patients may receive hydroxyurea (at any dose) or 1 dose of cytarabine (up to \leq 2g) prior to start of study treatment in order to keep their WBC at an acceptable level while being evaluated for the study. During the trial they may undergo leukopheresis for the same purpose.

Concomitant administration of any other therapy specific for MDS or AML, including any use of systemic retinoids, is prohibited. Concomitant administration of any other anticancer therapy is prohibited. Intrathecal chemotherapy is allowed, when indicated.

Subjects may receive anti-infective prophylaxis according to institutional practices. Use of recombinant myeloid colony stimulating factors (CSF) is allowed, if patients have febrile neutropenia or documented infections.

Concomitant medications will be recorded in the medical records only.

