10.0 Reporting of Adverse Events

These guidelines serve to bring the Department of Leukemia in compliance with the institutional policy on Reporting of Serious Adverse Events.

Adverse event is any untoward medical occurrence that may present during treatment with a pharmaceutical product but which does not necessarily have a causal relationship with this treatment. Adverse drug reaction is a response to a drug which is noxious and unintended and which occurs at doses normally used in man for prophylaxis, diagnosis, or therapy of disease or for the modification of physiologic function.

Assessing causal connections between agents and disease is fundamental to the understanding of adverse drug reactions. In general, a drug may be considered a contributory cause of an adverse event if, had the drug not been administered, 1) the event would not have happened at all, 2) the event would have occurred later than it actually did, or 3) the event would have been less severe.

Only unexpected AEs related to leukemia and events resulting in dose modification/delay will be recorded in the Case Report Form (CRF).

Expected events during leukemia therapy are:

- Myelosuppression related events (due to disease or leukemia therapy)
- Febrile or infection episodes not requiring management in the intensive care unit
- Epistaxis or bleeding except for catastrophic CNS or pulmonary hemorrhage
- Anemia, neutropenia, lymphopenia, thrombocytopenia, leukopenia
- Disease related events
- Symptoms associated with anemia (fatigue, weakness, shortness of breath)
- Electrolyte abnormalities (sodium, potassium, bicarbonate, CO₂, magnesium)
- Chemistry abnormalities (LDH, phosphorus, calcium, BUN, protein, albumin, uric acid, alkaline phosphatase, glucose)
- Coagulation abnormalities
- Disease specific therapy (induction, maintenance, salvage, or stem cell therapy)

- Alopecia
- Bone, joint, or muscle pain
- Disease progression
- Abnormal hematologic values
- General therapy related events
- Catheter related events
- Renal failure related to tumor lysis syndrome or antibiotic/ antifungal therapy
- Rash related to antibiotic use
- Hospitalization for the management of any of the above expected events
- Abnormal hematologic values will not be recorded on the case report form. For abnormal chemical values, the apogee or nadir (whichever is appropriate) will be reported per course on the case report form.

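### Section 5.11 b defines a hematologic DLT and then excludes it in the same paragraph without exception, and its grade wording literally leaves out Grade 4

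*Combined protocol and SAP*

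**What the plan says.** Section 5.11 has two items. Item a covers non-hematologic events. After a greater-than-or-equal sign it reads "grade 3 drug-related, clinically significant non-hematologic toxicities will be considered DLTs", and a list of common events that do not count follows.

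Item b covers hematologic events in three steps:

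- The criterion is "Grade 3 hematologic toxicity (criteria for leukemia on the CTC version 3.0) lasting for 6 weeks or more after interruption of therapy", together with a hypocellular marrow and no marrow blasts.
- A carve-out follows: "Anemia will not be considered a hematologic DLT".
- An exclusion list comes last. It is justified on the ground that the events occur in more than 50% of leukemia patients, and it says "they will not be used for the definition of MTD and DLT, nor will they be reported as ADRs: prolonged myelosuppression (grade 3 - 4". That first entry has no limit on duration, no marrow condition and no reference back to the criterion.

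Section 5.11 also says "See NCI Common Toxicity Criteria for definitions of DLT by organ system". Those criteria are not reproduced in the documents, so item b is the only hematologic DLT that the plan spells out.

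Sections 5.2 and 12.2 use the DLT count in a 3+3 rule that counts first-cycle DLTs only. Two or more DLTs close a dose level, and the MTD is the highest level with fewer than 2 of 6.

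**The concern.** A dose-decision rule needs a definition that two careful investigators would apply in the same way. Here one of them can count a patient with six weeks of blast-free marrow hypoplasia as a DLT under the criterion, and the other can discard the same patient under the exclusion. Each can point to the text.

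The DLT count decides whether a level is expanded, closed or called the MTD. The MTD sets the phase II dose (5.2 b) and, through Section 12.3, determines which chemo-naïve phase I patients are carried into the phase II analysis.

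**Working it through.** No figure in the plan is in dispute, so there is none to reproduce. The check sets the sentences of 5.11 b against each other and then follows one reclassified patient through the 3+3 rule.

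**Step 1: classification under each sentence of 5.11 b**

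| Patient | Criterion read literally | Exclusion list | Result |
|---|---|---|---|
| Grade 3 neutropenia or thrombocytopenia, 6 weeks or more after interruption, hypocellular, no blasts | DLT | not a DLT | contradiction |
| The same, but Grade 4 | not named | not a DLT | the more severe case is not a DLT |
| Grade 3 or 4 neutropenia or thrombocytopenia, under 6 weeks | not met | not a DLT | consistent |
| Anemia | carved out | – | consistent |

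The only rows in which the criterion has work to do are the rows in which the text fails.

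**Step 2: does the structure settle it?** Item a has the same form: a criterion, then a list introduced in the same way. There the list removes events from the criterion. Read in that way, item b removes its own criterion. Other entries in the two lists carry a qualifier: nausea and vomiting are excluded only if supportive care manages them, and readmission for cytopenia only if it is not fatal. Prolonged myelosuppression has none.

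**Step 3: does another section settle it?** Sections 5.2 and 12.2 use the term first-cycle DLT without defining it. Sections 5.6 and 10.0 treat myelosuppression as expected. Section 5.10.3 governs delay and discontinuation of nivolumab, not the DLT count.

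**Step 4: effect of one patient on the 3+3 decision (5.2, 12.2)**

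- 0 of 3 becomes 1 of 3: up to 3 more patients at the same level instead of escalation.
- 1 of 3 becomes 2 of 3: level closed instead of expanded.
- 1 of 6 becomes 2 of 6: level closed instead of open.
- 0 of 6 becomes 1 of 6: no change, level open.

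**Step 5: timing.** Six weeks is 6 × 7 = 42 days. A cycle is about 28 to 35 days (5.2). Whatever day of cycle 1 counts as the interruption, the criterion is met no earlier than day 1 + 42 = 43, which is after day 35. A criterion of this length therefore cannot normally be met within the first cycle. No sentence says whether an event that begins in cycle 1 and is confirmed later counts as a first-cycle DLT.

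**The case against.** The strongest reply is that the intent is clear. The exclusion is justified by events seen in more than half of leukemia patients, whereas six weeks of blast-free hypoplasia is much narrower. If all prolonged myelosuppression were excluded, the first sentence of item b would be empty and the anemia carve-out largely redundant. This stands as a statement of likely intent. It does not remove the contradiction, because the text never says that the criterion prevails.

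On the grade, the greater-than-or-equal sign is unreliable in this document. Section 4.1 defines high-risk MDS by 10% blasts where Sections 2.2 and 6.1 say at least 10%. Section 5.10.3 delays dosing for non-skin events above Grade 2 and then exempts Grade 2 fatigue, which makes sense only if Grade 2 was included. A sign lost in drafting or in text extraction is a live explanation, so the grade gap is the weaker half of the point. A reader might infer that Grade 4 was deliberately excluded, and nothing in the documents supports that.

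On weight, only nivolumab is escalated and the idarubicin and cytarabine doses are set by protocol. Section 5.6 states that nivolumab is not associated with myelosuppression. On that premise, prolonged hypoplasia would mostly reflect chemotherapy or disease and would say little about the nivolumab dose.

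Patients are also protected elsewhere. Section 5.10.3 says "Grade 3 drug-related thrombocytopenia > 7 days or associated with bleeding requires discontinuation" and stops nivolumab for nearly all Grade 4 drug-related events. SAEs go to the IND Office regardless of attribution (10.0). The Medical Monitor approves each dose change (12.2). Phase II monitors attributable grade 3 or 4 toxicity to 12 months (12.3). All of this stands and limits the harm, but none of it defines the DLT count.

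On timing, the cohort observation of about 3 weeks from first nivolumab (5.2) ends between day 22 + 21 = 43 and day 26 + 21 = 47, past the end of the cycle. How late a case would mature depends on which day counts as the interruption, and the text does not fix that day. No lag in days is claimed here.

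**Conclusion.** The contradiction in 5.11 b is real on the text and minor in effect. Followed literally, the paragraph cancels the only hematologic DLT that the plan writes out. The Grade 4 omission is also literal, but it may be a lost sign.

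Two stronger readings are tempting. One is that phase I has no working hematologic safety rule. The documents do not support it: the intended criterion can be recognized, Section 5.11 also points to outside criteria, and the safeguards above apply to each patient. The other is that the wrong dose is likely to go forward. The documents give no rate for prolonged hypoplasia, so any change in the probability of escalation would rest on an invented figure. What can be shown is that a single reclassified patient, in a phase I of at most 12, can change a dose decision.

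The exclusion from ADR reporting adds little, since Section 10.0 already says "Abnormal hematologic values will not be recorded on the case report form".

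**What to change.** In Section 5.11 b:

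1. After the entry for prolonged myelosuppression of grade 3 to 4, add: *except as defined in the first sentence of 5.11 b*.
2. In the criterion, replace Grade 3 with: *Grade 3 or higher*.

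Separately, the sponsor should decide, and write down, how an event that begins in the first cycle but is confirmed later is counted. A rule that closes a dose level retroactively or holds enrollment is not recommended here. Item b, unlike item a, does not require the toxicity to be drug-related, so such a rule could close a nivolumab level for chemotherapy-induced hypoplasia.

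The two wording changes are a one-paragraph amendment. They add no visits, no patients and no waiting time between cohorts.
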